3. PATIENT SELECTION

3.1 Inclusion Criteria (Modified 5/26/2020)

Patients can be of any race and either gender and must meet all of the following criteria to be eligible for participation in this study.

1. Patients must be 18 years of age or older
2. Patients with a confirmed diagnosis of AML or MDS, according to WHO classification (excluding acute promyelocytic leukaemia) with recurrent or refractory disease as defined below.
 - a. For AML:
 - (1) Primary induction failure (PIF) after \geq 2 cycles of chemotherapy.
 - (2) First relapse -only if occurring within 12 months from initial induction therapy.
 - (3) Relapse refractory to salvage chemotherapy
 - (4) Second or subsequent relapse.

Patients who fail targeted agents including IDH1, IDH2 or FLT3 inhibitors will be eligible if they fulfill other eligibility criteria.

Patients who fail venetoclax based therapy will be eligible if they fulfill other eligibility criteria.

- b. For MDS, either RAEB I or RAEB II who failed at least one chemotherapy regimen including either cytarabine or a hypomethylating agent.
Failure of cytarabine or hypomethylating agent will include patients who fail to achieve PR after four cycles of treatment.

Addendum 5/26/2020

Patients who fail targeted agents including IDH1, IDH2 or FLT3 inhibitors will be eligible if they fulfill other eligibility criteria.

Patients who fail venetoclax based therapy will be eligible if they fulfill other eligibility criteria.

3. Patients must have Karnofsky Performance score of \geq 70
4. Women of child-bearing potential must have a negative serum or urine pregnancy test within 2 weeks prior to treatment start
5. Patients must be capable of understanding and complying with protocol requirements, and must be able and willing to sign a written informed consent form

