7. CMV PCR, EBV PCR
8. HLA antibodies
9. Assessment of disease status (bone marrow, cytogenetics, molecular testing etc..) within 30 days prior to start of chemotherapy.
10. CRP, ESR (erythrocyte sedimentation rate), procalcitonin
11. Serum cytokine levels (IL1, IL6, TNF, TNFR1, REG3 alpha, ST2) (Samples to be drawn and stored for later analysis)

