9.0 CRITERIA FOR STUDY EVALUATION

- Responses must be maintained with no evidence of AML/MDS for more than four weeks. If chemotherapy continues, there can be no evidence of relapse within four weeks. Response assessments will require a bone marrow aspirate to be performed. In the event of a dry tap or an aspiration that is inadequate for interpretation, a bone marrow biopsy is required for response assessment.
- **Complete Remission (CR):** Complete remission is defined as all of the following:

- Peripheral Blood Counts:
 - Absolute neutrophil count $\geq 1000/\mu\text{L}$
 - Platelet count $\geq 100,000/\mu\text{L}$

- No leukemic blasts in the peripheral blood
 - Adequate erythroid recovery so that RBC transfusions are not necessary
- Bone Marrow:
 - Adequate cellularity
 - No Auer rods
 - < 5% blast cells
- No extramedullary leukemia (such as CNS or soft tissue involvement)

OR

- Complete Response with Incomplete Platelet Recovery (CRp): CRp satisfies all CR criteria except platelets < 100,000/ μ L, but platelet transfusions are not necessary
- **Partial Remission (PR):** Must meet all criteria of a CR except that the bone marrow may contain 5%-24% blasts
- **Treatment Failure:** Failure to achieve a CR (by 60 days after initial induction therapy started)
 - Treatment Failure Due to Resistant Disease:
 - Patients treated appropriately
 - Survived > 30 days after therapy began.
 - Failed to achieve remission due to persistent AML as determined by peripheral blood and bone marrow aspirate and biopsy.
 - Treatment Failure Due to Death of the Patient:
 - Patient died within 30 days of starting protocol therapy.
 - Record whether the patient died with or without evidence of persistent leukemia as determined by peripheral blood and bone marrow aspirate and biopsy.
- **Relapse** - Any of the following, occurring after either CR, CRp, or PR:
 - The reappearance of circulating blast cells not attributable to “overshoot” following recovery from myelosuppressive therapy
 - > 5% blasts in the marrow, not attributable to another cause (e.g., CSF, bone marrow regeneration)
 - Development of extramedullary leukemia

- **Toxicities will be followed using CTCAE criteria.**
Most toxicities will be attributable to the chemotherapy. Toxicity attributed to the cell infusions may include occurrence of GVHD and unexpected duration of myelosuppression. Severity of myelosuppression (hematologic toxicity) will not be taken into account.
- **Time to neutrophil recovery:**

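### Partial remission in section 9.0 requires no fall in marrow blasts from baseline, and the protocol does not settle whether PR counts as a response

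*Combined protocol and SAP*

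**What the plan says.** **Definition.** Section 9.0 says of PR: "Must meet all criteria of a CR except that the bone marrow may contain 5%-24% blasts". The criteria carried over from CR are:

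- ANC of at least 1000/µL and platelets of at least 100,000/µL;
- no leukemic blasts in the blood;
- red-cell transfusion independence ("Adequate erythroid recovery so that RBC transfusions are not necessary");
- adequate marrow cellularity and no Auer rods;
- no extramedullary leukemia.

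Neither this section nor any other compares the marrow with its pre-treatment state. Section 6.0, item 9, does ask for a disease assessment "within 30 days prior to start of chemotherapy".

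**Entry.** Section 3.1 admits AML with "Primary induction failure (PIF) after" at least two cycles, with early first relapse, with relapse refractory to salvage, or with a later relapse. It admits MDS that is "either RAEB I or RAEB II who failed at least one chemotherapy regimen including either cytarabine or a hypomethylating agent". It gives no marrow blast minimum and no blood count limits.

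**Status of PR.** Section 9.0 opens with a general rule: "Responses must be maintained with no evidence of AML/MDS for more than four weeks". It defines treatment failure as "Failure to achieve a CR (by 60 days after initial induction therapy started"). Its relapse item nevertheless lists PR beside CR and CRp as a state from which a patient can relapse, with a marrow threshold of more than 5% blasts. Section 11.1 names only CR or CRp as the protocol endpoint. Objective 1.2(e) covers response rates and duration without naming categories.

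**The concern.** A remission category should record a change in the disease. Here the marrow part of PR is a state that a patient may already be in on entry. The other PR criteria describe blood counts, transfusion need, blood blasts, marrow quality and extramedullary disease; none measures a change in marrow blast burden.

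The response rate is at stake. Response is a secondary objective, but section 10.1 (May 2020 addendum) enlarges the CBU cohort to 60 treated patients and presents that as enough to settle efficacy. No concurrent control is available: section 10 rules out a formal comparison between cohorts, and section 10.2 notes that the haplo cohort had not accrued. A reader will compare the rate with the historical series in section 2.1, which are reported as CR/CRp (none to 30%) or as CR (13%). A rate that included PR would not be like for like, and any PR given to unchanged disease would push it upward only.

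**Working it through.** **1. The plan's own figure.** The only precision statement is in section 10.1, for complications: n = 20, proportion 10%, 95% interval. The Wald half-width is 1.96 × √(0.10 × 0.90 / 20) = 0.1315, which agrees with the stated 13.1%. There is no corresponding figure or target for response, so nothing on response can be reproduced.

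**2. Fall in blasts needed to satisfy the blast part of PR.** For baseline blasts b (in %), the smallest relative fall that brings the marrow to the 24% ceiling is max(0, 1 − 24/b).

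| Baseline blasts | Fall needed |
|---|---|
| 6%, 10%, 19% or 24% | 0% |
| 30% | 20% |
| 48% | 50% |
| 60% | 60% |

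Anyone entering at 5%-24% meets the blast part with no change. A rise from 10% to 20% meets it too.

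**3. Can a patient enter in that range?** Yes, on the protocol's own terms. Section 3.1 has no blast floor, and section 9.0 lets relapse begin above 5% marrow blasts. RAEB I/II patients probably also fall in the range, but the documents give no blast limits for RAEB, so this is an assumption and the point does not need it.

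**4. Do the other criteria close the gap?** They narrow it. The patient must also meet every carried-over CR criterion. Since sections 3.1 and 3.2 set no count limits, that may be true at baseline or may follow from count recovery alone.

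**5. Is PR a response?**

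| Place | Reading |
|---|---|
| 9.0, four-week rule | Not a response, if 5%-24% leukemic blasts are evidence of disease |
| 9.0, treatment failure | Not a success: anything short of CR by day 60 is failure |
| 9.0, relapse | A response state, since relapse can follow it |
| 11.1 | Not the protocol endpoint |
| Objective 1.2(e) | Silent |

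In addition, a marrow above 5% and up to 24% lies in the PR range and also above the relapse threshold, so the duration of a PR has no clear meaning.

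**6. Size, if PR is counted.** One false PR adds 1/60 = 1.7 points in the CBU cohort, or 1/20 = 5 points in a cohort of 20. The expected inflation is f × (1 − r) × q, where f is the share entering with 5%-24% blasts, r is the true response rate, and q is the share of non-responders in that group who meet the rest of the PR definition. All three are assumptions.

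- Low end: f = 10%, r = 30%, q = 10% gives 0.10 × 0.70 × 0.10 = 0.7 points, or 0.4 patients of 60.
- High end: f = 40%, r = 10%, q = 50% gives 0.40 × 0.90 × 0.50 = 18 points, or 10.8 patients.

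A range this wide shows that the documents do not allow the effect to be sized.

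**The case against.** The strongest reply is that section 9.0 already keeps PR out of the response rate. Unchanged leukemic blasts fail the four-week rule, a patient without CR is a treatment failure, and section 11.1 recognises only CR or CRp. Response is also secondary and descriptive, and no test, threshold or stopping rule uses it. Most of this stands. A reader might infer that patients with unchanged disease will be scored as responders; the documents do not establish that. They do leave it open, because the relapse item treats PR as a response state and objective 1.2(e) does not exclude it.

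Three other inferences go too far:

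- *PR is decided by blood counts alone.* It is not. Blood blasts, transfusion need, cellularity, Auer rods and extramedullary disease also count, and these are demanding in relapsed or refractory patients after chemotherapy.
- *Every MDS patient meets the PR blast criterion on entry.* This needs RAEB cut-offs that the protocol does not give. The supported statement is that entry in the range is possible.
- *The definition distorts MDS eligibility.* Section 3.1 counts as failures patients who "fail to achieve PR after four cycles of treatment", but it says that failure includes them, not that it is limited to them. Nothing says that section 9.0 governs response to earlier treatment.

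**Conclusion.** The point holds in a limited form. The blast part of PR needs no improvement for a patient entering at 5%-24%, entry in that range is permitted, and the remaining criteria can be met without any change in marrow disease. A stated rule can therefore label unchanged disease a partial remission. Whether this reaches the reported response rate depends on whether PR is counted, and the protocol contradicts itself on that.

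If PR is counted, the bias is upward: 1.7 points per false PR at n = 60. The number of false PRs is unknown, because the documents give neither the baseline blast distribution nor the share of patients with adequate counts. The preliminary results cited as section 2.6 were not in the text available, so how responses were counted there could not be checked.

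The primary safety objective rests on grade III-IV GVHD and prolonged myelosuppression and is untouched. The point should be corrected because the cohort was enlarged with efficacy in view and the correction is cheap.

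**What to change.** 1. Define the response rate for objective 1.2(e) as CR+CRp. This matches section 11.1 and the CR/CRp benchmarks in section 2.1, and by itself removes the possible bias from the headline rate.
2. Report PR on a separate line only. Require a stated fall in marrow blasts from the pre-chemotherapy assessment (section 6.0, item 9), so that a patient already meeting PR at baseline cannot be scored PR without that fall. A fall of at least 50% is one option; it is a proposal and does not come from the documents. With that figure, PR would be unattainable for anyone entering below 10%, since half of 9% is 4.5%, already under the 5% floor. The amendment should say that this is intended or choose another threshold.
3. State what applies where the baseline marrow was waived because circulating blasts were 10% or more (section 7.1 footnote). Clearance of blood blasts, which PR already requires, could document the change.
4. Reconcile PR with the four-week rule, the treatment failure definition and the relapse threshold of more than 5% blasts, so that one patient cannot be in PR, failure and relapse at once.

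**Cost.** Amendment wording and re-scoring of some PR cases from assessments already required, including the marrow due by day 60 (section 7.4). No new procedure is needed. The reported PR rate may fall slightly.

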	HLA 5/6 matched graft			HLA 4/6 matched graft		
	TNC2.5	TNC1.5	TNC0.5	TNC2.5	TNC1.5	TNC0.5
AAFA	0.20	0.51	0.74	0.77	0.98	1.00
AFB	0.19	0.51	0.73	0.76	0.98	1.00

CARB	0.20	0.52	0.74	0.76	0.98	1.00
SCAMB	0.23	0.54	0.74	0.78	0.98	1.00
AINDI	0.35	0.70	0.86	0.86	0.99	1.00
FILII	0.32	0.72	0.89	0.83	0.99	1.00
HAWI	0.25	0.57	0.76	0.78	0.97	1.00
JAPI	0.29	0.68	0.87	0.83	0.99	1.00
KORI	0.32	0.70	0.88	0.85	0.99	1.00
NCHI	0.33	0.72	0.89	0.85	0.99	1.00
SCSEAI	0.30	0.65	0.83	0.85	0.99	1.00
VIET	0.32	0.69	0.86	0.83	0.99	1.00
MENAFC	0.42	0.74	0.88	0.89	0.99	1.00
EURCAU	0.63	0.89	0.96	0.95	1.00	1.00
CARHIS	0.36	0.70	0.86	0.87	0.99	1.00
MSWHIS	0.40	0.75	0.89	0.89	0.99	1.00
SCAHIS	0.40	0.74	0.88	0.89	0.99	1.00
AISC	0.50	0.79	0.90	0.91	0.99	1.00
ALANAM	0.42	0.73	0.88	0.89	0.99	1.00
AMIND	0.50	0.80	0.92	0.92	1.00	1.00
CARIBI	0.30	0.62	0.81	0.83	0.99	1.00

Population	Broad race	Description
AAFA	AFA (African American)	African American
AFB		African
CARB		Black Caribbean
SCAMB		Black South or Central American
AINDI	API (Asian or Pacific Islander)	South Asian
FILII		Filipino
HAWI		Hawaiian/other Pacific Islander
JAPI		Japanese
KORI		Korean
NCHI		Chinese
SCSEAI		Other Southeast Asian
VIET		Vietnamese
MENAFC		Mideast/North Coast of Africa
EURCAU	CAU (Caucasian)	European Caucasian
CARHIS		Caribbean Hispanic
MSWHIS	HIS (Hispanic)	Mexican or Chicano
SCAHIS		South or Central Amer. Hispanic
AISC		Amer. Indian South or Central America
ALANAM	NAM (Native American)	Alaska Native or Aleut
AMIND		North American Indian
CARIBI		Caribbean Indian

In this initial study, we propose to utilize either haplo-identical cells or CBU cells depending on availability and our selection criteria. This will allow us to compare in a preliminary fashion the toxic (GVHD, myelosuppression, development of HLA antibodies to the donor) and therapeutic effects (count recovery, response rate) of each of these products.

The biological effects of the CBU infusions is immunologically and largely T-cell mediated. Moderate doses of T-cells as low as $0.2-1 \times 10^6$ CD3/kg_{recipient} have been associated with beneficial effects in the adoptive therapy of viral diseases and likely also mediate GVL effects.²³ Approximately 30 % of the cellular content of a CBU unit consists of Tcells. CBU with a cell dose as low as 5×10^6 /kg_r nucleated cells will be permissible. The highest acceptable nucleated cell dose will be 25×10^6 /kg_r

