8.3 Recording and Reporting of Adverse Events and SAEs

- Safety reporting will be 21 CFR 312.32 compliant.
- Salvage chemotherapy for AML/MDS is a complex procedure with the possibility of prolonged initial admission and numerous immediate and delayed complications as well as frequent readmissions.
- **Expected toxicities are those listed in the consent form and include regimen-related toxicities, myelosuppression, opportunistic infections, haplo-immunostorm, engraftment syndrome and GVHD. These will be captured in the transplant database and reported to the IRB on a quarterly basis**
- **Unexpected** adverse events are those leading to ICU admission or to death. Such toxicities will be reported immediately to the designated study chairman. Such events will be reported to the local IRB within the institution's prescribed time period.

	Immediate Reporting	Report quarterly
Hematopoietic Toxicity	Death	Time to Hematopoietic recovery
Extramedullary Toxicity	Fatal toxicity and toxicity requiring ICU admission	Grade III-IV toxicities not requiring ICU admission
Infections	Fatal or requiring ICU admission	Grade II-IV
Acute GVHD	Fatal or Grade IV	Grade II-IV
Chronic GVHD	Fatal or requiring ICU admission	Limited and extensive
Haplo-immunostorm and/or engraftment syndrome	Fatal or requiring ICU admission	All others.

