The first of three consecutive days with ANC $>5 \times 10^9/L$.
- **Time to platelet recovery;**
Platelet recovery is reported when the platelet count is $\geq 20 \times 10^9/L$ seven days after platelet transfusion and is maintained for three consecutive lab values obtained on different days.
- **Treatment Related Mortality**
Considered any death that cannot be explained by persistence, relapse or progression of the underlying malignancy once the preparative regimen starts.
- **Acute GVHD**
Acute GVHD will be scored according to the criteria proposed by Przepiorka et al.²⁸
Risk score for acute GVHD will be further assigned based on recent publication by Mac Millan et al.²⁹
Chronic GVHD will be scored according to the consensus criteria.³⁰

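### Section 9 as supplied dates neutrophil recovery from an ANC above 5 × 10^9/L, five times the ANC it requires for remission

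*Combined protocol and SAP*

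**What the plan says.** All the definitions involved stand in Section 9.0, Criteria for Study Evaluation.

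- Time to neutrophil recovery: "The first of three consecutive days with ANC $>5 \times 10^9/L".
- CR, neutrophils: "Absolute neutrophil count $\geq 1000/\mu\text{L". CR, platelets: "Platelet count $\geq 100,000/\mu\text{L".
- CRp: "CRp satisfies all CR criteria except platelets", so the neutrophil requirement is the same as for CR.
- PR: "Must meet all criteria of a CR except that the bone marrow may contain 5%-24% blasts", so the neutrophil requirement is again the same.
- Platelets: "Platelet recovery is reported when the platelet count is $\geq 20 \times 10^9/L$ seven days after platelet transfusion", maintained over three consecutive laboratory values.

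Recovery is used elsewhere. Section 2.4 lists, among the effects to be described for the two cell products, "therapeutic effects (count recovery, response rate) of each of these products". The reporting table in Section 8.3 puts "Time to Hematopoietic recovery" in the quarterly column.

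Section 10 restricts the safety endpoint to two complications. The second is unexplained myelosuppression in which counts have not recovered more than 30 days after chemotherapy ended, with no leukaemia or MDS found. An incidence above 10% is called unacceptable, and Section 10.2 gives the complication its own stopping row. Neither section states a count, names a cell line or refers to Section 9.

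**The concern.** Recovery is normally an earlier and easier milestone than remission, which adds marrow and blood-blast criteria to the counts. The platelet definitions here follow that order. The neutrophil definitions reverse it: the cut-off for calling neutrophils recovered lies well above the count that suffices for CR.

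Two things are at stake. The first is direct: time to neutrophil recovery is an operational definition, and applying it as printed gives misleading times, including for patients in remission. The second is indirect. Section 10 needs some meaning for *count recovery*, and Section 9 holds the only definition of neutrophil recovery in the documents. Section 9 also says that cell-infusion toxicity may include an unexpected duration of myelosuppression and that its severity is not counted. Duration cannot be measured without a recovery criterion.

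**Working it through.** **The plan's own figure.** The one calculation that involves the myelosuppression endpoint is the ±13.1% in Section 10.1, for 20 patients and a 10% proportion:

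1.96 × √(0.10 × 0.90 / 20) = 1.96 × 0.0671 = 0.1315.

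It reproduces. It contains no count threshold, so it neither supports nor is harmed by the neutrophil cut-off.

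**Common units.** One litre is 10^6 µL.

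- Neutrophil recovery: 5 × 10^9 / 10^6 = 5000/µL.
- CR platelets: 100,000/µL × 10^6 = 100 × 10^9/L.

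| Cell line | Recovery cut-off | CR count | Recovery ÷ CR |
|---|---|---|---|
| Neutrophils | >5000/µL | ≥1000/µL | 5000 / 1000 = 5 |
| Platelets | ≥20 × 10^9/L | ≥100 × 10^9/L | 20 / 100 = 0.2 |

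**Which responses are affected.** CRp relaxes only the platelet count and PR only the marrow blasts. All three response categories therefore keep ANC ≥1000/µL, and the factor of 5 applies to each.

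**Effect on recovery times.** Any run of three days above 5000/µL is also a run of three days at or above 1000/µL. The printed rule therefore can never give an earlier date than the same rule set at the CR count. It gives the same date or a later one, and no date at all for a patient whose ANC settles between 1000 and 5000/µL. The delay in days cannot be derived, because the documents give no count trajectories.

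**Section 10, by illustration.** Take a hypothetical leukaemia-free patient on day 31 after chemotherapy, with ANC 1.5 × 10^9/L and platelets 60 × 10^9/L, both sustained without transfusion.

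- By the Section 9 recovery definitions, platelets have recovered (60 ≥ 20) and neutrophils have not (1.5 < 5).
- By the CR counts, neutrophils pass (1.5 ≥ 1.0) and platelets do not (60 < 100).

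Section 10 does not say which comparison decides, or whether one cell line or both must recover. The example shows that the wording is open. It does not show that any patient was scored wrongly.

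**The case against.** Five arguments count against the point.

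1. *The figure may be a reading fault.* The whole discrepancy rests on one number, and a decimal could have been lost when the PDF was read. Decimals in the same notation do survive elsewhere (the minimum cord blood cell dose in Section 5.3 prints as 0.5 × 10^7/kg), but that does not prove this one is intact. The objection stands, and is why the fix starts with the source file.

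2. *Remission and recovery are different endpoints.* Unequal cut-offs are not in themselves a contradiction. That is true, but it does not explain a recovery cut-off above the remission count next to a platelet pair in the opposite order. No other section gives a value that overrides the printed one.

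3. *The outcome is minor.* Time to recovery is not among the objectives in Sections 1.1 and 1.2, Section 10 rules out formal comparison of the cohorts, and the May 2020 addendum says the haplo-identical cohort had not accrued. This stands and lowers the severity. Quarterly reporting remains.

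4. *The link to the safety endpoint is inferred.* A reader might conclude that well patients in remission will be counted as myelosuppression events and push a cohort over its stopping boundary. The documents do not support that. Section 10 does not cite the Section 9 definition; it speaks of life-threatening, attributable and unexplained complications, which argues against scoring such a patient; and Section 12 makes the study chairman final arbiter of toxicity. Those words still supply no threshold.

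5. *The stopping looks are past for the cord blood cohort.* The table in Section 10.2 ends at 20 patients, and the addendum reports no rule met after more than 30. This stands: nothing suggests that the printed value drove a decision. The addendum does not say which criterion was used.

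**Conclusion.** The point holds in a limited form. As supplied, the neutrophil recovery cut-off is 5 times the ANC required for CR, CRp and PR, while the platelet cut-off is 0.2 times its CR count. Applied as written, the definition gives recovery times that are overstated or never reached, even for patients in remission. This is a faulty operational definition, provided that the figure is printed this way in the source file.

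The missing meaning of *count recovery* in Section 10 is a separate gap and would remain if the figure proved to be a reading fault. On its own it is mainly missing detail. An effect on the primary safety result or on the stopping rule is not shown, and its size cannot be derived: the documents do not say how many leukaemia-free patients would stay at an ANC of 1.0 to 5.0 × 10^9/L beyond day 30.

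Severity: should be fixed. Confidence is medium, because of the possible lost decimal.

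**What to change.** 1. Check the neutrophil recovery figure against the source file. If it differs from the text supplied, only step 3 remains.
2. If it is printed as supplied, reconcile the recovery and response definitions in Section 9 so that the neutrophil recovery cut-off does not exceed the ANC required for CR.
3. State in Section 10 that *count recovery* uses the reconciled Section 9 definitions, and whether it covers neutrophils, platelets or both.
4. Only if the printed cut-off was applied, re-derive the recovery times from the counts already collected, and check any myelosuppression scoring that relied on it. Exact dating may not be possible: the schedule in Section 7.1 requires a blood count only at least twice weekly up to day 60, while the neutrophil rule needs three consecutive days. Report how many patients can be dated and how the gaps were handled.

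The cost is one corrected line and one cross-reference. Step 4 adds work on existing data, limited by how often counts were taken. Sample size and the numbers in the stopping table do not change.

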7.0 REQUIRED DATA

7.1 Pre-Study Testing Intervals

To be completed within 30 DAYS before infusion of stem cells:

- All bloodwork
- History and physical
- bone marrow

All others to be completed within 42 DAYS before infusion of stem cells:

Tests & Observations on patient	Prior to infusion of stem cells	Day 0-Day 60	Beyond day 60 (only if evidence of donor chimerism)
Informed Consent	X		
History and Progress Notes	X	A ☺	E
Physical Examination	X	A ☺	E
Height	X		
Weight/Body Surface Area	X		
Karnofsky Performance Status	X		E
Drug Toxicity Assessment		B	
GVHD/Engraftment Syndrome assessment		B	E
Laboratory Studies			
CBC, Differential, Platelets	X	A	E
Serum Chemistry **	X	B	E
Uric Acid	X		E
Magnesium	X		E
PT (INR), PTT, Fibrinogen	X		
Urinalysis	X		
EBV PCR	X	B	E
CMV PCR	X	B	
Lymphocyte subsets (laboratory tests 17603138 and 17603144)	X	D	E
Chimerism Peripheral Blood	X	C	E
ESR, CRP, procalcitonin	X	D	E
HLA antibodies	X		F
CMV antibody test, hepatitis panel (HepA Ab, HepB Sab, HepB Sag, HepB Core Ab, HepC Ab), herpes simplex, syphilis, HIV and HTLV 1 antibody, and varicella zoster virus	X		
Chest x-ray or Chest CT	X		
Staging			
Bone Marrow Asp,biopsy with cytogenetic and Flow and chimerism†	X***	Before day 60	
Correlative Laboratory studies			
Microchimerism*		C	E
Serum Cytokine level ((IL1, IL6, TNF, TNFR1, REG3 alpha,	X*	D*	E*

Tests & Observations on patient	Prior to infusion of stem cells	Day 0-Day 60	Beyond day 60 (only if evidence of donor chimerism)
ST2) (sample stored for subsequent analysis)			

† A bone marrow biopsy is required for response assessment in the event of a dry tap or an aspiration that is inadequate for interpretation.

A: At least twice weekly.

B: At least weekly starting on day of infusion

C: Weekly until day 60. Every two months thereafter until one year after cell infusion.

D: Every two weeks until Day 60. Lymphocyte subsets are performed only at Day 28.

E: At least monthly until Day 180 and at least every two months thereafter until one year. Lymphocyte subsets are performed only at Day 100, Day 180, and 1 year.

F: Performed only at Day 100 • Physical exam and history will focus on signs and symptoms of GVHD

*microchimerism assays will be performed in selected cases of CBU infusion and based on HLA type of recipient, CBU unit and Mother of the CBU donor.

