10. STATISTICAL CONSIDERATIONS

The primary objective of this study is to evaluate the safety of adoptive immunotherapy with IPA targeted CBU or with haplo-identical stem cells after conventional induction therapy for very high risk AML or MDS.

The study has 2 cohorts. Patients in cohort 1 will receive CBU cells as adoptive immunotherapy. Patients in cohort 2 will receive haplo identical cells. Both cohorts will be evaluated separately and no formal statistical comparison between cohorts will be performed in this pilot study.

Reinduction therapy in patients with recurrent AML and MDS is extremely toxic with high induction related mortality, which is however justified by the dismal prognosis of patients who don't receive treatment. Safety of the adoptive immunotherapy will be defined as absence of life threatening complications attributable to the adoptive immunotherapy part of the protocol. These are restricted to: 1) grade III-IV GVHD; an incidence of $>10\%$ of this complication in either cohort will be considered unacceptable. 2) Unexplained prolonged myelosuppression, i.e. no count recovery for more than 30 days after completion of chemotherapy, without evidence of residual or recurrent leukemia/MDS. An incidence of $>10\%$ of this complication will also be considered unacceptable.

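### The minimum CBC frequency does not guarantee the three consecutive daily neutrophil counts that the definition of neutrophil recovery needs

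*Combined protocol and SAP*

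**What the plan says.** Section 9.0 defines time to neutrophil recovery as "The first of three consecutive days with ANC" above a printed threshold. The platelet definition directly below it is built differently: the count must reach its level and "is maintained for three consecutive lab values obtained on different days".

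In the Section 7.1 schedule, the row "CBC, Differential, Platelets" has code A for Day 0 to Day 60: "A: At least twice weekly". Beyond Day 60, and only where there is evidence of donor chimerism, it has code E: "E: At least monthly until Day 180 and at least every two months thereafter until one year". The protocol states no CBC frequency for inpatients and no rule for days on which no count was taken.

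Section 8.3 lists "Time to Hematopoietic recovery" among the items reported quarterly. Section 10 makes unexplained prolonged myelosuppression one of two primary safety complications, described as "no count recovery for more than 30 days after completion of chemotherapy" without residual or recurrent disease, and treats an incidence above 10% as unacceptable. Section 10 does not refer to the Section 9.0 definitions and does not say which cell line must recover.

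**The concern.** The neutrophil definition is written in calendar days, but the schedule guarantees only two counts a week. A patient sampled at or near that minimum on regular weekdays may have an ANC above the threshold at every draw and still have no date that meets the definition. A patient with daily counts and the same true course would have one. Whether recovery is dated would then depend partly on sampling intensity.

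Duration is what the protocol intends to measure here. Section 9.0 names unexpected duration of myelosuppression as a toxicity of the cell infusion and sets its severity aside, and Section 2.4 lists count recovery among the effects to be looked at for each product. If site staff fill the gap with an unwritten rule, dates may not be comparable across patients. If the same definition also decides count recovery in Section 10, a recovered patient without a date could be counted as a primary safety event.

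**Working it through.** **Plan's own figure.** The plan gives none on this point. Its one precision figure, ±13.1% in Section 10.1, reproduces as 1.96 × √(0.10 × 0.90 / 20) = 0.131. It is not in dispute and does not change.

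**Inputs.** Recovery needs three adjacent days (Section 9.0). CBCs are at least twice weekly to Day 60 (Section 7.1). The cell product is given 24 to 72 hours after chemotherapy (Section 5.2). The cohort size is about 20, later raised to 60 treated for CBU (Section 10.1). Two myelosuppression cases stop a cohort at 5 or at 10 treated (table in Section 10.2).

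**Step 1: counts at the minimum.** From Day 0 to Day 60 there are 60 / 7 × 2 ≈ 17 CBCs. The 30-day limit in Section 10 falls at about Day 27 to Day 29 (30 minus 3 days to 30 minus 1 day). By then about 28 / 7 × 2 = 8 counts are required.

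**Step 2: can those counts cover three adjacent days?** Three adjacent days fall on three different weekdays. A patient drawn on the same two weekdays each week is sampled on only two, so the answer is no. Listing every choice of k fixed weekdays out of seven, and letting runs cross the week boundary, gives:

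| CBCs per week | Patterns with a run of 3 or more days | All patterns |
|---|---|---|
| 2 | 0 | 21 |
| 3 | 7 | 35 |
| 4 | 21 | 35 |
| 5 | 21 | 21 |
| 6 | 7 | 7 |
| 7 | 1 | 1 |

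A Monday/Wednesday/Friday pattern exceeds the minimum and still has no run of three. All patterns succeed only from five draws a week.

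**Step 3: weekdays that vary.** If the two draws may move from week to week, runs across the boundary become possible. Over two adjacent weeks there are 21 × 21 = 441 combinations. A run of three needs either the last two days of week one plus the first day of week two (6 combinations) or the last day of week one plus the first two days of week two (6), with one combination in both: 6 + 6 − 1 = 11. This counts patterns; it is not a probability. It shows that a run is rare at the minimum but not impossible.

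**Step 4: the platelet wording under the same schedule.** On a Monday/Thursday pattern, three consecutive values are Monday, Thursday, Monday. Twice-weekly sampling can therefore meet a rule based on values. It spans 7 days, and the gaps between draws are 3 and 4 days.

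**Step 5: weight of one patient, if Section 9.0 governs Section 10.** 1/60 = 1.7 percentage points; 1/20 = 5 percentage points. These are the weight of any single patient, not estimates of bias. The documents do not say how many patients are sampled near the minimum before recovery.

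**The case against.** The strongest reply is that the schedule sets a floor. Daily counts comply with it, and Section 8.3 anticipates that the initial admission may be prolonged, so many patients may have dense counts through recovery. That stands. A reader might infer that a patient followed exactly to schedule can never be recorded as recovered. The documents do not support this: it holds only at or near the minimum, on regular weekdays, with consecutive days read literally.

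A reader might also infer that outpatients would be scored as unrecovered and that this would push the primary complication rate over 10% or stop a cohort. That is not supported either. Section 5.1 allows hypomethylating agents but does not say where they are given. Section 10 does not tie count recovery to Section 9.0, and its event must also be unexplained. Section 12 has investigators score patients weekly during admission and makes the study chairman the final arbiter where opinions on toxicity differ. Nothing suggests that a patient with satisfactory counts at every draw would be scored as having a life-threatening complication. The May 2020 addendum in Section 10.2 reports that the stopping rules had not been met in the CBU cohort after more than 30 patients, so its early looks are past. The haplo-identical cohort had not accrued, so there the early triggers still lie ahead.

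What remains is that the definition asks for data the schedule does not secure, and no rule says what to do when they are absent. The lack of a link between Sections 9.0 and 10 limits the consequence but is itself a gap: Section 9.0 holds the only definitions of neutrophil and platelet recovery, so without them count recovery in Section 10 is undefined.

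**Conclusion.** The point holds as a mismatch between a definition and the sampling it relies on. At the minimum CBC frequency on fixed weekdays, no patient can be given a neutrophil recovery date under the literal rule (0 of 21 patterns); at three draws a week most patterns still fail (28 of 35). The result clearly affected is time to hematopoietic recovery, which becomes partly a function of how often blood is drawn.

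The effect on the primary safety component is conditional on the Section 9.0 definition being used to decide count recovery in Section 10, which the protocol does not state. On that assumption each misclassified patient counts for 1.7 points at 60 patients or 5 points at 20. The number affected is unknown and may be small if most patients have frequent counts until recovery. No sample size or precision figure changes. The correction is worth making because it is cheap and affects a reported result.

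**What to change.** Define neutrophil recovery as the first of three consecutive laboratory values, obtained on different days, above the ANC threshold. This takes its unit from the platelet definition, and stating that the first of the three is the recovery date makes the dating explicit. Then state in Section 10 whether this rule decides count recovery for the myelosuppression component and, if not, what does. Apply the rule to counts already collected, so that all CBU patients are measured alike.

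This change should leave the threshold and its inequality alone. Separately, the printed value of more than 5 × 10^9/L must be reconciled with the complete remission criterion in the same section, at least 1000/µL (1 × 10^9/L), which is one fifth of it.

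The cost is one line in Section 9.0, one sentence in Section 10 and no extra blood draws. With twice-weekly sampling the date is known only to within about 3 to 4 days, and confirmation takes about 7 days from the first qualifying value, against 2 days with daily counts. Some dependence on sampling frequency therefore remains, but every patient whose counts stay above the threshold can be given a date.
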